Potential participants (both cases and controls) will be identified from the antenatal, obstetric medical and day assessment clinics at Queen Charlotte's and Chelsea Hospital, St Mary's Hospital and other participating units. Midwives and clinicians will be able to refer women who have previously had the conditions after asking them if they would be interested in speaking to someone from the research team regarding the study. Posters will be used in clinical areas and in the cafe area by the antenatal clinic to highlight the research. Women will also be approached directly in these clinics by researchers.

Non-pregnant females may be identified through organisations such as ICP Support and from posters in gynaecology clinics and hospital areas such as the entrance lobby to the main hospital where the shop and cash machine is situated. Clinicians and nurses will

also be able to refer women to the research team after asking the patient if they would be interested in speaking to someone from the research team.

The study will be a case-control study. The pregnancy cohort will be recruited prospectively and will undergo longitudinal study. The non-pregnant participants will also be recruited prospectively but this will be a cross-sectional study.

The study will comprise of the following groups of women. In the groups that comprise pregnant women, maternal blood will be collected at delivery together with placental samples and cord blood (once delivery has taken place and the cord has been clamped and cut). The collection of these types of samples will allow the researchers to fully investigate the metabolites, bile acids and hormones implicated in the disorder together with the potential impact they may have on both mother and baby.

Group 1 are non-pregnant women who have either had normal pregnancies in the past or who have had at least one pregnancy affected by intrahepatic cholestasis of pregnancy (ICP) and/or gestational diabetes mellitus (GDM). This group should only have to attend the study for one day.

Group 2 are women who are identified in early pregnancy. They are either expected to go on to have normal pregnancies or are women with a previous history of ICP and/or GDM. These women may be asked to participate up to three times. This will mean they will need to attend for three separate days. However, this will be linked to their regular visits to the hospital.

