An **adverse event (AE)** is any untoward medical occurrence in a participant during the study participation days. An existing medical condition (unless it worsens on the study participation days) is not classed as an AE.

All AEs will be recorded in the notes of the participant and on an AE form

A **serious advent event (SAE)** is any untoward and unexpected medical occurrence or effect that:

- Results in death
- Is life threatening to mother and/or baby
- Requires hospitalization
- Results in persistent or significant disorder incapacity ability

All SAEs and action taken as a result will be recorded in the notes of the participant and on an SAE form. An SAE form should be completed and faxed to the Chief Investigator within 24 hours. All SAEs should be reported to the appropriate research ethics committee where in the opinion of the Chief Investigator, the event was:

- 'related' i.e. resulted from the administration of any research procedures; and
- 'unexpected', i.e. an event that is not listed in the protocol as an expected occurrence

Reports of related and unexpected SAEs should be submitted within 15 days of the Chief Investigator becoming aware of the event using the NRES SAE form for non-IMP studies.

Contact details for reporting SAEs

[name] – [name]

[contact] Attention: URGENT - [name]

Please send SAE forms to [name], Dept of Surgery & Cancer, [name]

It is not anticipated that there will be any increased risk of adverse events or serious adverse events in this study. However, it could be that a participant may have an unexpected reaction to the food they eat i.e. an allergic reaction and appropriate action will need to be taken in the event of this happening.

It is also possible that a participant may experience a vasovagal (fainting) episode during venepuncture and appropriate care of the participant will be implemented should this happen.

7. Statistics

- Data analysis will take place at the Institute of Reproductive and Developmental Biology, Imperial College, London. It will be undertaken by the research scientists with statistical advice from the divisional statistician.
- We will use conventional statistical analysis including tests of normal distribution and either Students T-test or the Mann-Whitney U test as appropriate.

8. Procedure for entry to the study, schedule for sample analysis and data recording

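### The SAE definition in Section 6 includes expectedness, so a serious event judged expected needs no SAE form and no 24-hour report

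*Protocol*

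**What the plan says.** All the relevant text is in Protocol Section 6, Adverse Events.

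- **AE definition.** An adverse event "is any untoward medical occurrence in a participant during the study participation days". Expectedness plays no part in it.
- **AE recording.** "All AEs will be recorded in the notes of the participant and on an AE form". No time limit is given.
- **SAE definition.** An SAE "is any untoward and unexpected medical occurrence or effect that" leads to death, threatens the life of mother or baby, requires hospitalisation, or causes lasting or significant incapacity.
- **SAE recording and reporting.** "All SAEs and action taken as a result will be recorded in the notes of the participant and on an SAE form". The form then goes by fax to the Chief Investigator inside 24 hours.
- **Ethics-committee reporting.** The Chief Investigator decides which SAEs were both related and unexpected, and those are reported within 15 days. Unexpected here means "an event that is not listed in the protocol as an expected occurrence".
- **Foreseen reactions.** The section closes with two possibilities. One is an allergic reaction to the food, which it describes with the word 'unexpected'. The other is that "a participant may experience a vasovagal (fainting) episode during venepuncture", which it calls possible without saying whether it is expected.

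**The concern.** Seriousness and expectedness are separate questions. Seriousness should decide whether the Chief Investigator hears of an event quickly. Expectedness, together with relatedness, should decide whether the ethics committee hears of it. Section 6 applies expectedness at both steps.

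What is at stake is the order of judgement. The section gives the expectedness decision to the Chief Investigator at the ethics-committee step. By also putting it in the definition, it requires a decision before the form exists. The protocol does not say who makes that earlier decision. In practice it would be whoever decides whether to complete an SAE form, possibly at one of the other participating centres allowed for in Section 4. An event set aside at that point need not reach the Chief Investigator within 24 hours, so there may be no prompt opportunity to disagree.

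**Working it through.** There is no figure to reproduce. The check sets the rules of Section 6 side by side and follows each kind of serious event through them.

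**Step 1: the rules as written.**

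- SAE = untoward, and unexpected, and at least one of the four seriousness criteria.
- SAE form and 24-hour fax: required if the event is an SAE.
- Ethics-committee report: required if the event is an SAE and, in the Chief Investigator's opinion, related and unexpected.

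**Step 2: apply them to untoward events that meet a seriousness criterion.**

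| Serious event is | SAE form and 24-hour fax, as written | Ethics committee, as written | SAE form and 24-hour fax, without 'and unexpected' | Ethics committee, without 'and unexpected' |
|---|---|---|---|---|
| unexpected, related | yes | yes | yes | yes |
| unexpected, unrelated | yes | no | yes | no |
| expected, related | **no** | no | **yes** | no |
| expected, unrelated | **no** | no | **yes** | no |

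The table assumes that the two expectedness judgements agree. Deleting the words changes only the two expected rows, and only the route to the Chief Investigator. The ethics-committee column stays the same.

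**Step 3: is the second expectedness test doing any work?** If the word means the same in both places, every SAE has already passed the test, and only relatedness still selects among SAEs. If it means something different, the definition uses a term that the section does not explain, because the only explanation given belongs to the ethics-committee criterion. On either reading the word does not belong in the definition.

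**Step 4: what is left for a serious event judged expected.** On a study participation day it still meets the AE definition, so it goes in the notes and on an AE form. What it loses is the SAE form and the 24-hour route. No deadline applies to the AE form.

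**Step 5: the two foreseen reactions.**

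- *Allergic reaction to food.* The section itself uses the word 'unexpected' for it. One that led to hospitalisation would be untoward, unexpected and serious, and therefore an SAE with form and fax.
- *Faint at venepuncture.* It is named as possible, with no label. The ethics-committee criterion turns on whether the protocol lists an event as expected, and the protocol has no explicit list. Whether being mentioned here amounts to being listed cannot be settled from the text.

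**The case against.** **The benign reading.** The only explanation of the word is that an event is unexpected unless the protocol lists it as expected. There is no such list, so it can be argued that every serious event is unexpected, every one is an SAE, and nothing is missed. This is the strongest defence, and it shows that the gap depends on how staff read the section. It does not remove the gap. The definition does not refer to that explanation, the faint is named in the same section, and a reporting rule should not depend on the absence of a list.

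**Redundancy is not contradiction.** Two tests that share a word make the second partly redundant, and the ethics-committee step still adds relatedness and the Chief Investigator's own view. That is fair. The fault is a misplaced condition, not two rules that cannot both be followed. It is also fair that a site-level judgement of expectedness is inferred, since the protocol assigns that judgement only to the Chief Investigator.

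**Events are still recorded.** This stands for study participation days. The loss is of prompt reporting, not of all recording.

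**Stronger readings that the text does not support.**

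- A reader might infer that both foreseen reactions fall outside the SAE route even when serious. They do not: the allergic reaction is called unexpected and is captured, and the faint is ambiguous rather than excluded. No proportion of missed events can be stated.
- A reader might also fault the seriousness list for omitting prolongation of an existing stay. The protocol states no such criterion elsewhere that the list would contradict, and Group 3's frequent attendance consists of visits, not admissions.
- A reader might infer that sampling at delivery falls outside the AE window, because Section 4 says that "maternal blood will be collected at delivery". The protocol does not define study participation days as excluding delivery, and the SAE definition carries no such day limit. This is missing detail, not an error.

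**Low risk.** The study-day procedures are blood sampling and standard meals, with allergy needs taken into account, and Section 6 anticipates no increased risk. That limits the number of events affected but gives no reason to keep the wording.

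**Conclusion.** The point holds as a defect in the definition. As written, a serious event judged expected is not an SAE and needs neither the SAE form nor the 24-hour report, and the later expectedness test becomes redundant. The inconsistent treatment of the allergic reaction and the faint leaves staff without a clear guide to what counts as expected.

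The size is qualitative. Of the four kinds of serious event in the table, the two expected ones lose the 24-hour route and the two unexpected ones are unaffected. The protocol gives no event rates, so the number of events cannot be estimated. Given the procedures it is probably small. No endpoint, sample size or analysis is touched.

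The conclusion rests on reading the definition literally and on someone other than the Chief Investigator applying it first. If every site treated all serious events as unexpected for lack of a list, nothing would be missed in practice, but the wording does not secure that.

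**What to change.** In Section 6:

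1. Delete 'and unexpected' from the SAE definition, so that any untoward occurrence meeting a seriousness criterion gets an SAE form and the 24-hour report.
2. Keep expectedness only in the ethics-committee reporting criterion, where the Chief Investigator judges it.
3. State at that criterion whether the allergic reaction and the faint count as expected occurrences, and bring the closing paragraphs of the section into line with that statement.

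This is a wording amendment, with a matching check of the SAE form. Under Sections 9.1 and 9.6 it needs the approval of the investigators, the sponsor and Trust R&D, and review by the ethics committee. The running cost is at most a few more SAE forms, and recruitment and analysis are unaffected.

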9.1. Ethical Approval

Prior to starting the study, we will seek ethical approval from NHS Research Ethics Committee (NHS REC). Amendments to the protocol will be made with the approval of the chief / principal investigator(s) and will be subject to review by the REC. The study will be carried out in accordance with the Declaration of Helsinki.

9.2. Consent

For participants recruited at Queen Charlotte's and Chelsea Hospital and St Mary's Hospital a member of the research team will meet with the participant to explain the study to them and to answer any questions that they may have. They will have as much time as they need to think about the study and will be given an information sheet to take home to look at, together with a letter explaining what happens next should they wish to take part, a medical questionnaire (which they will need to complete to check eligibility) and a pre-paid envelope. Following this, the participant will be given an appointment to come in to hospital to be formally recruited to the study and sign a consent form

Participants recruited via the patient organisation will be sent an information sheet about the study via email/post. This gives them time to consider whether they are interested in taking part. If they are, they will be sent a letter acknowledging their interest and giving them the opportunity to ask any questions about the research. The letter will also include a consent form and a medical questionnaire. If they need to discuss the study they will be contacted at a time to suit them. Following this they will be asked to sign the consent form and return it to us in the post together with the completed questionnaire.

In addition to a written information sheet, all women will be provided with contact details for members of the research group and will be encouraged to make contact should they have any questions or concerns about the study. It will be made explicit to the participants that they can change their mind about taking part at any stage of the recruitment process and during the research period itself.

9.3. Confidentiality

The Chief Investigator will preserve the confidentiality of participants taking part in the study and is registered under the date Protection Act

9.4. Indemnity

Imperial College holds negligent harm and non-negligent harm insurance policies which apply to this study.

9.5. Sponsor Imperial College London will act as the main sponsor for this study. Delegated responsibilities will be assigned to the NHS trusts taking part in this study.

9.6 Trust R&D Any amendments should also be approved by the sponsor and Trust R&D department.

9.7. Funding

The study has been funded by The Wellcome Trust and is also supported through internal funding.

Participants will be awarded (in vouchers) £20 for every study day they take part in, up to a potential maximum of £60.

